10.4.6 Pharmacokinetic assessments

Blood samples for PK assessments must be collected at the time points specified in the SoP (Section 4). Note that at Week 15, a blood sample for PK will be drawn but no assessments that require trial personnel will be performed.

Collection, handling and shipment instructions for PK blood samples are provided in a laboratory manual.

Serum samples for determination of tralokinumab concentrations will be analysed by a laboratory using a validated bioanalytical method. Details of the analytical method used will be described in the bioanalytical report.

Samples will be retained for as long as the quality of the material permits evaluation but for no longer than 12 months after completion of the clinical trial report (CTR).

10.4.7 Anti-drug antibodies measurements

Blood samples will be collected for determination of anti-tralokinumab antibody levels at pre-determined time points according to the SoP (Section 4).

Collection, handling and shipment instructions for ADA blood samples are provided in a separate laboratory manual.

Serum samples for determination of presence or absence ADA will be analysed by a laboratory using a validated bioanalytical method. A tiered testing scheme will be employed, with the first step being screening. Samples found positive in the screening step will be tested in the confirmatory step. Samples confirmed positive for ADA in the confirmatory step will undergo ADA endpoint titre determination and will be analysed for the presence of

Trial ID: LP0162-1325	Date: 14-Aug-2018	Version: 4.0
		Page 79 of 169

neutralising antibodies (nAB). Details of the analytical method used will be described in the ADA bioanalytical report.

Samples will be retained for as long as the quality of the material permits evaluation but for no longer than 15 years after marketing authorisation.

10.5 Other assessments and photography

10.5.1 Skin microbiology

10.5.1.1 Background and rationale

Normal skin is colonised by a wide variety of microorganisms, including fungi, viruses, and bacteria. The skin microbiome is complex and diverse, and varies between individuals and anatomical sites (37). It has been known for years that some skin diseases are associated with dysbiosis of the skin microbiome. AD, in particular, has long been associated with increased skin colonisation with S. aureus. Indeed, S. aureus colonisation has been proposed to play an important role in AD pathophysiology via bacterial production of specific virulence factors (38). Increased colonisation with S. aureus in AD is accompanied by decreased colonisation with many commensal bacterial species, resulting in overall decreases in bacterial diversity (39). Resolution of active disease in AD in response to therapy correlates with reduction of S. aureus colonisation and increases in microbiome diversity (39).

A recent phase 2b trial in subjects with moderate-to-severe AD who were sampled with skin swabs on lesional skin showed a reduced frequency of S. aureus positive subjects following treatment with tralokinumab compared with placebo. A similar evaluation will be performed in the present trial. Since global analyses of microbiome diversity were not undertaken in the phase 2b tralokinumab trial, the present trial will use gene sequencing to identify specific strains of bacteria present on the skin and thus characterise treatment effects on the skin microbiome in AD subjects.

10.5.1.2 Staphylococcus aureus colonisation (all subjects)

Samples (skin swabs) from a representative lesion will be taken from all subjects to detect presence or absence of S. aureus colonisation. Samples will be collected according to the SoP (Section 4) and the body location will be documented in the eCRF (upper limb, lower limb, trunk, head). Efforts will be made to swab the same skin site (lesion) at all time-points, even if the lesion has cleared.

S. aureus colonisation will be determined using an RNA-based method (quantitative real-time polymerase chain reaction). This will provide data on treatment effects on subclinical infections with S. aureus that is very frequent in AD patients.

Collection, handling and shipment instructions for skin swabs are provided in a separate laboratory manual.

10.5.1.3 Skin microbiome characterisation (selected trial sites)

At selected trial sites, subjects will be asked to participate in an exploratory component involving skin microbiome characterisation. Participation in this exploratory component which also includes skin biopsies and additional serum biomarker testing requires that the subject provides additional informed consent.

Skin swabs will be taken from a representative lesion. Samples will be collected according to the SoP (Section 4) and the same lesion will be sampled throughout the trial. The location of the lesion will be documented in the eCRF (upper limb, lower limb, trunk). Isolates will be cultured and the microbiome will be characterised using next-generation sequencing.

Subjects should not shower, bathe, or otherwise wash the lesion where the swab will be taken from within 12 hours of sample collection.

Collection, handling and shipment instructions for skin swabs are provided in a separate laboratory manual.

Since subjects will also have skin biopsies taken from the lesion selected for microbiome characterisation, the trial will provide a unique opportunity to combine gene expression, histology, and microbiome data from the same lesions in AD subjects. The results will help to clarify the role of IL-13 pathways in regulation of the skin microbiome and may shed light on the role of the microbiome in the pathophysiology of AD.

The skin microbiome results will not be included in the CTR but will be presented in a separate report.

10.5.2 Serum biomarkers

10.5.2.1 Rationale

Serum biomarkers will be evaluated as an exploratory part of the tralokinumab phase 3 programme to profile the molecular response and to identify subpopulations of AD patients with increased response to treatment.

Collection, handling and shipment instructions for biomarker samples are provided in a separate laboratory manual.

Trial ID: LP0162-1325	Date: 14-Aug-2018	Version: 4.0
		Page 81 of 169

The biomarker results from the small panel will be presented in the CTR, whereas results from the large panel (assessed at selected trial sites) will be presented in a separate report.

10.5.2.2 Small biomarker panel (all subjects)

All subjects will have blood samples taken for analysis of a small panel of biomarkers. The biomarkers to be analysed include, but are not limited to, the following: periostin, DPP4, CCL17 (also known as thymus and activation regulated chemokine [TARC]), IL-13, IL-17, IL-22, and beta-defensin 4A (DEFB4A). These samples will be taken according to the SoP (Section 4). LEO may only analyse samples from a subset of subjects.

10.5.2.3 Large biomarker panel (selected trial sites)

At selected trial sites, subjects will be asked to participate in additional biomarker testing. Participation in this component of the trial which also includes skin microbiome characterisation and skin biopsies requires that the subject provides additional informed consent.

Subjects consenting to additional biomarker testing will have an extra blood sample taken to measure additional serum biomarkers. These samples will be taken according to the SoP (Section 4). To allow unbiased biomarker discovery, a large panel of biomarkers will be assessed.

10.5.3 Skin biopsies (selected trial sites)

At selected trial sites, subjects will be asked to participate in an exploratory component involving skin biopsies. Participation in this component of the trial which also includes skin microbiome characterisation and additional serum biomarker testing requires that the subject provides additional informed consent.

Two 3 mm skin biopsies (1 for histology, 1 for gene expression analysis) must be taken from lesional skin at the time-points specified in the SoP (Section 4). At baseline, 2 skin biopsies will also be taken from non-lesional skin at an anatomically similar site (i.e., a total of 4 biopsies at baseline). The lesional skin biopsies must be taken from the same lesion used for microbiome characterisation (Section 10.5.1.3). The body location of each site will be documented in the eCRF (upper limb, lower limb, trunk).

A check of skin biopsy wound healing including removal of suture, if applicable, will be performed at the next trial visit (i.e., at Weeks 2, 6, and 18).

Collection, handling and shipment instructions for skin biopsy samples are provided in a separate laboratory manual.

Trial ID: LP0162-1325	Date: 14-Aug-2018	Version: 4.0
		Page 82 of 169

The biopsies will be analysed for expression of markers of inflammation and skin barrier integrity by histology/immunohistochemistry and gene expression analysis.

The biomarkers to be analysed include, but are not limited to, the following:

Histology/immunohistochemistry/in-situ hybridisation

 T cells (e.g., CD3+ and CD8+), dendritic cells (e.g., CD11c+, FccR1), monocytes/macrophages (e.g., CD68), epidermal markers (e.g., epidermal thickness, keratin type I cytoskeletal 16, proliferation marker protein Ki-67, protein S100-A, filaggrin, loricrin).

Gene expression analysis

- Global gene expression analysis by RNA sequencing.
- Quantitative real-time polymerase chain reaction (qPCR) analysis of the following genes: IL-1B, IFNG, IL-13, IL-31, CCL17 (TARC), CCL26, C-X-C motif chemokine ligand 10 (CXCL10), IL-12/IL-23p19, IL-17A, CCL20, IL-19, IL-20, IL-22, S100A9, S100A12.

Rationale for selection of biomarkers in biopsies

The biomarkers to be analysed in the biopsies have been selected to assess the effect of IL-13 inhibition on cell types and cytokines that play a key role in AD skin. Effective treatments of AD are known to reduce the number of inflammatory cells in lesional skin as well as to modulate epidermal markers towards a non-diseased phenotype (25). A quantitative real-time polymerase chain reaction analysis of markers of specific subsets of T cells (e.g., Th1, Th2, Th17, and Th22) will allow analysis of the mechanism of action of tralokinumab in diseased AD skin.

Overall, the results from the analyses of biopsy material will be included in the CTR, except the global gene expression analysis which will be presented in a separate report.

10.5.4 Storage of biological samples

Samples collected as part of the exploratory component (microbiome characterisation, biomarkers, and skin biopsies) will be retained for as long as the quality of the material permits evaluation but for no longer than 12 months after completion of the CTR unless specific additional consent has been obtained that allows storage for future research (see below).

Biobank

This protocol includes the collection and analysis of different biological samples. If consent is given by the subject, LEO will store samples collected as part of the exploratory component

(i.e., serum samples for biomarker analysis and skin biopsies) in the biobank established by LEO and hosted by BioStorage Technologies, Inc. The residual biological samples will be used for future research performed by LEO. Donation of the samples for future research is voluntary and subjects must give their separate written consent to confirm donation and storage and the terms associated herewith. The samples will be transferred from the relevant laboratory to the biobank. The samples will be labelled with the trial ID, subject ID, and the sample date to protect the privacy of the subjects and to allow continued blinding for future analyses. The samples from this trial will be stored for 10 years after the end of the trial and will then be destroyed.

10.5.5 Photography (selected trial sites)

At selected trial sites, subjects will be asked to participate in a photography component involving digital photography assessments to show disease progression over time.

Participation in this photography component requires that the subject provides additional informed consent.

Digital colour photographs will be taken of the disease area and a representative lesion according to the SoP (Section 4).

The trial sites will use their own equipment to take the photographs. Instructions for photography will be provided to the sites in a photography manual. Photography standards and procedures are provided to the trial sites by the central photography vendor.

The photographs will have no other subject identifier than the subject ID and will be transmitted electronically to the photography vendor using a secure file transfer protocol.

Printed copies of the photographs must be included as part of the individual subject source documentation.

LEO may at its discretion use the photographs in publications, posters and similar types of information material or media targeting patients and HCPs. The photographs can also be part of training material used for training and educational purposes. Steps will be taken to ensure that the identity of the subject is protected to the extent possible.

10.6 Estimate of total blood volume collected

Blood samples will be drawn for safety (chemistry, haematology, serology, PK, ADA) and biomarkers. The total volume of blood to be withdrawn is approximately 435 mL which is less than the volume of blood drawn during a blood donation (approximately 500 mL).

11Adverse events

AEs and serious adverse events (SAEs) are defined in Appendix 2.

Classification of AEs in terms of severity, causality and outcome are defined in Appendix 3.

11.1 Collection of adverse events

AEs must be collected from time of first trial-related activity after the subject has signed the informed consent form until completion of the clinical trial (defined as the safety follow-up visit 16 weeks after last injection). For subjects entering the long-term extension trial (LP0162-1337, ECZTEND), any (S)AE with onset before the final visit in the LP0162-1325 trial should be reported LP0162-1325. If ongoing, the (S)AE will also be recorded as medical history in ECZTEND.

AEs must be assessed by medically qualified personnel.

At all visits, the subject will be asked a non-leading question by the investigator about AEs, for example: "How have you felt since I saw you last?" No specific symptoms should be asked for. It is important that the investigator also observes the subject for any changes not reported by the subject and records these changes.

Refer to Appendix 4D for principles for data entry in the eCRF.

11.2 Reporting of adverse events

AEs reported by the subject or observed by the investigator must be recorded on the AE form of the CRF and should be described in the following manner:

The *AE term* must be in precise English medical terminology (i.e. not necessarily the exact words used by the subject). Whenever possible, a specific diagnosis should be stated (for example 'allergic contact dermatitis').

The *duration* of the AE must be reported by the start date and stop date of the event. In addition, it must be recorded whether the AE started prior to start of IMP.

AEs must be classified in terms of severity, causality and outcome according to the definitions in Appendix 3.

Action taken with trial treatment: Any action taken with IMP as a consequence of the AE must be recorded (dose not changed, dose reduced, dose increased, drug interrupted, drug withdrawn, not applicable, unknown).

Trial ID: LP0162-1325	Date: 14-Aug-2018	Version: 4.0
		Page 85 of 169

Other action taken: any other action taken as a result of the AE must be recorded (none, concomitant medication, concomitant procedure).

Withdrawn due to AE: it must be recorded whether the AE leads to withdrawal from the trial.

11.3 Reporting of serious adverse events

The criteria that define an AE as serious (i.e., an SAE) are defined in Appendix 2.

11.3.1 Investigator reporting responsibilities

Any SAE must be reported to LEO on the (paper) SAE Form within 24 hours of first knowledge. This report should contain an assessment of available information on seriousness, severity, causal relationship to the IMP, comparator or trial procedure, the action taken, the outcome to date, and a narrative description of the course of the event.

The completed SAE form must be faxed or scanned and e-mailed to Global Pharmacovigilance, LEO using the e-mail address or fax number below:

Global Pharmacovigilance, LEO

E-mail address: [contact]

[contact]

It may be relevant for the investigator to enclose other information with the SAE form, such as anonymised reports of diagnostic procedures, hospital records, autopsy reports, etc.

Additionally, Global Pharmacovigilance, LEO may request further information in order to fully assess the SAE. The investigator must forward such information to LEO upon request by fax or e-mail (see contact details above).

The investigator must notify the local institutional review board(s) (IRB[s])/ independent ethics committee(s) (IEC[s]) of SAEs as required by current applicable legislation for the concerned country.

SAEs occurring after the completion of the clinical trial (i.e., after the safety follow-up visit [FU1/FU2]) should not be routinely sought or collected. However, such events should be reported to LEO (see contact details above) if the investigator becomes aware of them.

11.3.2 LEO reporting responsibilities

Global Pharmacovigilance, LEO is responsible for assessing whether or not an SAE is expected. The relevant reference document for this clinical trial is:

For the IMP, the Investigator's Brochure, edition 16 and subsequent updates must be used.

Global Pharmacovigilance, LEO will notify the regulatory authorities and concerned investigators of SAEs according to the current applicable legislation for the concerned countries.

The IRB(s)/IEC(s) will be notified of SAEs according to the current applicable legislation for the concerned countries.

For all countries except the US, all SAEs which are assessed as causally related to the IMP(s) by either the investigator or LEO (ICH E2A Guideline), and which are unexpected (Suspected, Unexpected Serious Adverse Reactions [SUSARs]), are subject to expedited reporting to regulatory authorities and IRB(s)/IEC(s) according to the current applicable legislation in the concerned countries. Investigators will be notified of such SUSARs and the evolving safety profile on an ongoing basis.

For the US, as per Guidance for Industry and Investigators - Safety Reporting Requirements for INDs and BA/BE Studies, only those events for which the sponsor determines there is a reasonable possibility of a causal relationship are subject to IND Safety Reporting. Investigators will be notified of the evolving safety profile on an ongoing basis.

11.4 Other events that require expedited reporting

11.4.1 Pregnancy

Any pregnancy occurring during the clinical trial must be reported to LEO within 24 hours of first knowledge using the (paper) Pregnancy Follow Up Form (Part I). All such pregnancies must be followed up until delivery or termination and final outcome must be reported on the (paper) Pregnancy Follow Up Form (Part II) within 24 hours of first knowledge.

The completed Pregnancy Follow Up Forms must be faxed or scanned and e-mailed to Global Pharmacovigilance, LEO. Contact details are given in Section 11.3.1.

Pregnant subjects must permanently discontinue IMP (see Section 9.8.1).

11.5 Reporting of other events

11.5.1 Adverse events of special interest

The events listed in Panel 14 are considered adverse events of special interest (AESIs) in this trial and will require that the investigator provides additional information to LEO. An AESI may be serious (requiring expedited reporting, Section 11.3) or non-serious.

Adverse event of special interest	Additional information to be provided (if available ¹)
Eczema herpeticum	 Skin findings: Lesion type. Disseminated / localised. Location. Present in an area with visible eczema / no visible eczema / present in areas with and without eczema. Monomorphic / polymorphic. Confirmation of herpes simplex virus
Malignancies diagnosed after randomisation, excluding basal cell carcinoma, localised squamous cell carcinoma of the skin, and carcinoma in situ of the cervix	Histology report Oncology assessment Treatments (surgery, radiation, chemotherapy, other)
Skin infections requiring systemic treatment	Skin swab Outcome.
Conjunctivitis	Aetiology (viral, bacterial, allergic, unknown) Bacterial culture outcome (for events with bacterial aetiology) Diagnosis confirmed by ophthalmologist
Keratoconjunctivitis	Aetiology (infectious, non-infectious, other, unknown) Bacterial culture outcome (for events with bacterial aetiology) Diagnosis confirmed by ophthalmologist

Panel 14 Adverse events of special interest

Trial ID: LP0162-1325	Date: 14-Aug-2018	Version: 4.0
		Page 88 of 169

Adverse event of special interest	Additional information to be provided (if available ¹)	
Keratitis	Aetiology (infectious, non-infectious, other, unknown) Bacterial culture outcome (for events with bacterial aetiology) Diagnosis of herpes simplex keratitis (for events with viral aetiology) Diagnosis confirmed by ophthalmologist	

¹The additional data to be recorded in the eCRF are not a requirement, but are to be reported by the investigator, if available, for example as part of standard clinical practice.

11.5.2 Overdose

An overdose is defined as a subject receiving a dose of IMP in excess of that specified in this protocol.

The term overdose must be documented on the AE form of the CRF. In addition, AEs originating from overdose must be documented on a separate line.

LEO does not recommend specific treatment for an overdose. The investigator will use clinical judgment to treat any overdose if necessary.

11.5.3 Medication error

Medication error refers to any unintentional error in the dispensing or administration of an IMP while in the control of the investigator or subject. Broadly, medication errors fall into four categories: wrong medication, wrong dose (including strength, form, concentration, amount), wrong route of administration, or wrong subject.

The medication error must be documented on the AE form in the eCRF. In addition, AEs originating from a medication error must be documented on a separate line specifying the category of error (see definitions above).

If the medication error is due to device malfunction, such malfunction must be reported as a device complaint as described in Section 9.11.

11.5.4 Misuse

Misuse refers to situations where the IMP is intentionally and inappropriately used not in accordance with the protocol.

Trial ID: LP0162-1325	Date: 14-Aug-2018	Version: 4.0
		Page 89 of 169

The term misuse must be documented on the AE form in the eCRF. In addition AEs originating from misuse must be documented on a separate line.

11.5.5 Abuse

Abuse relates to the sporadic or persistent, intentional excessive use of an IMP which is accompanied by harmful physical or psychological effects.

The term abuse must be documented on the AE form in the eCRF. In addition, AEs originating from abuse must be documented on a separate line.

11.5.6 Aggravation of condition

Any clinically significant aggravation/exacerbation/worsening of any medical condition(s), compared to screening, must be reported as an AE.

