12.3.7.1 Adverse events

AEs will be coded during the course of the trial according to Medical Dictionary for Regulatory Activities (MedDRA). AEs will be presented by preferred terms and primary system organ class (SOC).

Treatment-emergent AEs will be summarised, however, all AEs recorded during the course of the trial will be included in the subject data listings. An event will be considered treatment-emergent if started after the first use of IMP or if started before the first use of IMP (applicable if subject had a wash-out) and worsened in severity thereafter. The tabulations described in the following will only include the treatment-emergent events. In each of the tabulations, AEs will be defined by MedDRA preferred terms within primary SOC.

An overall summary of the number of treatment-emergent AEs, number (percentage) of subjects with any treatment-emergent AEs, SAEs, deaths, premature discontinuations from the trial due to AEs, treatment-related AEs and severe AEs will be presented.

The number of AEs and the number of subjects experiencing each type of AE will be tabulated by treatment group. The percentage of subjects with AEs in the initial treatment period will be compared between treatment groups by a chi-square test or Fisher's exact test (if expected cell count < 5).

The severity for each type of AE will be tabulated by treatment group.

The causal relationship to IMP for each type of AE will be tabulated by treatment group.

Related AEs are defined as AEs for which the investigator has not described the causal relationship to IMP as 'not related'. The number of related AEs and the number of subjects experiencing each type of related AE will be tabulated. The percentage of subjects with related AEs in the initial treatment period will be compared between treatment groups by a chi-square test or Fisher's exact test (if expected cell count <5).

SAEs and AESIs will be evaluated separately. A narrative for each SAE will be given. AESIs and AEs leading to withdrawal from trial will be tabulated and listed.

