Appendix 2: Definitions of adverse events and serious adverse events

Adverse event definition

An AE is defined as any untoward medical occurrence in a patient or clinical investigation subject administered a pharmaceutical product and which does not necessarily have a causal relationship with this treatment. An AE can therefore be any unfavourable and unintended sign (including an abnormal laboratory finding), symptom, or disease temporally associated with the use of a medicinal (investigational) product, whether or not related to the medicinal (investigational) product. (ICH Harmonized Tripartite Guideline for Good Clinical Practice, E6 (R1)).

This definition includes:

 accidental injuries, events related to trial procedures, reasons for any unfavourable and unplanned change in medication (drug and/or dose), clinically significant worsening of pre-existing conditions, or reasons for admission to hospital or surgical procedures unless these were planned before enrolment. It also includes AEs commonly observed and AEs anticipated based on the pharmacological effect of the IMP. In addition, any laboratory abnormality assessed as clinically significant by the investigator must be recorded as an AE.

Serious adverse event definition

An SAE is any untoward medical occurrence that

- results in death.
- is life-threatening.
- requires inpatient hospitalisation or prolongation of existing hospitalisation. Planned hospitalisation or planned prolonged hospitalisation do not fulfill the criteria for being an SAE but should be documented in the subject's medical record.
- results in persistent or significant disability/incapacity.
- is a congenital anomaly/birth defect.

or

• is a medically important condition. Events that may not be immediately lifethreatening or result in death or hospitalisation but may jeopardise the subject or may require intervention to prevent one of the other outcomes listed in the definition above. Examples are intensive treatment in an emergency room or at home for allergic bronchospasm, blood dyscrasias and convulsions that do not result in hospitalization, development of drug dependency or drug abuse.

Trial ID: LP0162-1325	Date: 14-Aug-2018	Version: 4.0
		Page 126 of 169

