Appendix 4D: Record keeping, quality control, and data handling

Case report forms

Data will be collected by means of electronic data capture unless transmitted to LEO or designee electronically (e.g., laboratory data). The investigator or staff authorised by the investigator will enter subject data into electronic CRFs. Data recorded in the eCRFs will be accessible to the trial site and LEO personnel immediately after entry. The CRFs must be maintained in an up-to-date state by the trial site at all times.

The investigator must verify the correctness of the data entered by the site by electronically dating and signing all CRFs used. This signature information will be kept in the audit trail and cannot be altered. Any correction(s) made by the investigator or authorised site staff to the

Trial ID: LP0162-1325	Date: 14-Aug-2018	Version: 4.0
		Page 131 of 169

CRF after original entry will be documented in the audit trail. Changes to data already approved will require the re-signature by the investigator. The person making the change to the data, and the date, time and reason for the change will be identified in the audit trail.

Principles for data entry

Clinically significant abnormal findings at the (first) screening visit will be documented as medical history in the eCRF.

If an abnormal finding (vital signs, physical examination, laboratory tests, ECG) at any other visit than the (first) screening visit is considered by the investigator to be clinically significant, it will be reported as an AE in accordance with Section 11.2. Further, any clinically significant deterioration of a pre-existing condition as well as any new clinically significant sign, symptom or illness observed after screening will be reported as an AE in accordance with Section 11.2.

Source data

For all data recorded, the source document must be defined in a source document agreement or similar document at each trial site. There must only be one source defined at any time for any data elements.

Source data should as a general rule be recorded in the subject's medical record or other defined document normally used at the trial site. Source data not normally collected as a routine part of the clinical practice at the site may be entered on a worksheet. Clinical assessments/safety evaluations must be signed by medically qualified investigators.

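### Clinically significant worsening of atopic dermatitis counts as an adverse event, so the pooled between-arm AE comparison mixes harm with lack of efficacy and can dilute an excess of other events

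*Protocol*

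**What the plan says.** Protocol 11.5.6 sets the reporting rule: "Any clinically significant aggravation/exacerbation/worsening of any medical condition(s), compared to screening, must be reported as an AE". The AE definition in Appendix 2 includes "clinically significant worsening of pre-existing conditions", and the data-entry principles in Appendix 4D require reporting of "any clinically significant deterioration of a pre-existing condition as well as any new clinically significant sign, symptom or illness" seen after screening. None of these exempts AD, which every subject has.

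Protocol 12.3.7.1 describes the analysis. Only treatment-emergent events are tabulated: "The tabulations described in the following will only include the treatment-emergent events". An event that began before the first dose and then became more severe also qualifies. On the comparison between arms it says "The percentage of subjects with AEs in the initial treatment period will be compared between treatment groups by a chi-square test", or by Fisher's exact test when expected counts are small. A second test follows: "The percentage of subjects with related AEs in the initial treatment period will be compared between treatment groups". The overall summary also has a line for severe AEs. On detail it says "In each of the tabulations, AEs will be defined by MedDRA preferred terms within primary SOC", and SAEs and AEs of special interest are evaluated separately.

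SAP 6.7.1 covers assignment of AEs to periods and the sort order of tables. It sets no AD terms aside.

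**The concern.** A subject whose AD becomes clinically worse than at screening has an AE under this rule. The same course can make that subject an efficacy failure, because rescue treatment leads to non-responder status (Protocol 9.7 and 12.3.5.1.1). Elsewhere the protocol keeps the two ideas apart: Section 8.5 records lack of efficacy and AE as different reasons for discontinuation.

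The design gives the rule room to act. The reference visit is screening, but topical corticosteroids and calcineurin inhibitors must be stopped for the two weeks before randomisation, and the EASI entry threshold is 12 at screening and 16 at baseline. AD can therefore be milder at the reference visit than at first dose.

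If tralokinumab works, AD-worsening AEs should be fewer in that arm. A pooled percentage of subjects with any AE then moves in the drug's favour for reasons of efficacy. Similar pooled percentages could be taken as evidence of no added harm when part of the similarity comes from fewer AD events.

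**Working it through.** **Inputs from the documents.** 585 and 195 subjects (Protocol 12.1); two-sided 5% level (12.3.10); chi-square comparison (12.3.7.1). The numbers randomised stand in for the safety analysis set.

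**Inputs assumed.** The documents give no AE rate of any kind. Let h be the risk of at least one AE other than AD worsening and a the risk of an AD-worsening AE, taken as independent within each arm. Subscript P is placebo and T is tralokinumab.

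**Formulas.** Any AE = 1 − (1 − h)(1 − a). For a difference d = p_T − p_P, power in the harm direction is Φ[(d − 1.96·SE0)/SE1]. SE0 uses the pooled proportion and SE1 the separate proportions.

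**Reproducing the plan's own figure.** For IGA 0/1 at 30% versus 10%, the pooled proportion is 0.25, SE0 = √(0.25 × 0.75 × (1/195 + 1/585)) = 0.0358 and SE1 = √(0.10 × 0.90/195 + 0.30 × 0.70/585) = 0.0286. Then (0.20 − 1.96 × 0.0358)/0.0286 is about 4.5, and power exceeds 99%, as Protocol 12.1 states. EASI75 at 40% versus 15% also reproduces.

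**Applied to AEs, with h_P = 50% and h_T = 60%:**

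| AD-worsening AEs, placebo / tralokinumab | Any AE, placebo | Any AE, tralokinumab | Difference (points) | Power to show the excess |
|---|---|---|---|---|
| none | 50.0% | 60.0% | +10.0 | 69% |
| 10% / 10% | 55.0% | 64.0% | +9.0 | 61% |
| 10% / 5% | 55.0% | 62.0% | +7.0 | 41% |
| 20% / 10% | 60.0% | 64.0% | +4.0 | 17% |
| 25% / 10% | 62.5% | 64.0% | +1.5 | 6% |
| 30% / 10% | 65.0% | 64.0% | −1.0 | 1% |

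Example, fourth row: 1 − 0.50 × 0.80 = 0.60 and 1 − 0.40 × 0.90 = 0.64. Simulation with 20,000 trials per row gave the same answers to within rounding. With the same 10-point excess and h_P = 40% or 60%, power without AD events is 68% or 73%. With AD events in 20% and 10% it is 11% or 27%.

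**Cancellation.** The pooled difference is zero when a_P = 1 − (1 − h_T)(1 − a_T)/(1 − h_P). With a_T = 10% and a 10-point excess, a_P must be 25%, 28% or 32.5% for h_P of 40%, 50% or 60%. The gap in AD events is then 15, 18 or 22.5 points.

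**Opposite error.** With no difference in other AEs (50% in each arm) and AD events in 25% on placebo and 10% on tralokinumab, any AE is 62.5% and 55.0%. In simulation, tralokinumab was significantly lower in about 45% of trials.

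**Dependence.** If AD events occur only in subjects who also have another AE, there is no dilution. If no subject has both, 20% and 10% cancel the excess exactly (50 + 20 = 70 and 60 + 10 = 70). Independence lies between these.

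**Why preferred-term rows do not settle it.** If A subjects have any AE and B have AD worsening, the number with at least one other AE lies anywhere from A − B to A. In the placebo arm of the fourth row, A = 0.60 × 195 = 117 and B = 0.20 × 195 = 39. The answer lies between 78 and 117, or 40% to 60%.

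**The case against.** Several stronger conclusions are tempting, and the documents do not support them.

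- A reader might infer that every flare is an AE. The rule covers only clinically significant worsening relative to screening. Subjects already have IGA of at least 3 and EASI of at least 12 at screening, so a flare that stays within screening severity is outside it. Rescue use is not equated with an AE either.
- A reader might take the planned IGA 0/1 rates of 30% and 10% as the size of the imbalance. Those are response rates. A placebo subject who stays at IGA 3 is a non-responder without an AE. They support the expected direction, not its size.
- A reader might infer that drug benefit will cancel a real excess of harm. Under independence that needs an AD-event gap of 15 to 22.5 points, and neither document gives such a rate. Smaller gaps give dilution.
- A reader might infer that AD events cannot be seen apart. They have their own preferred-term row, with severity and causality by arm, and SAEs and events of special interest are evaluated separately. A specific harm is not hidden; only the pooled percentages are affected.
- Related AEs may be less affected. Appendix 3 directs events better explained by the subject's clinical state to the not-related category, which would remove many disease flares.

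Two further points have weight. The test sentence follows one on types of AE and could be read as a test for each type; other terms would then be unmixed. The AE tests are also unpowered and outside the multiplicity procedure. Finally, moving the test wholly to non-AD events would drop any drug-induced AD worsening. That argues for adding a comparison, not replacing one.

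What remains is that, on the pooled reading, the percentage mixes two opposing quantities, and no planned output gives the unmixed one.

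**Conclusion.** The point holds for the pooled between-arm comparison of subjects with AEs. The mixing follows from the text alone; its size does not. Assuming independent event types and a 10-point excess of other AEs (60% versus 50%), a 5-point lower AD-event rate on tralokinumab cuts power from 69% to 41%, and a 10-point lower rate cuts it to 17%. The bias favours the drug if AD-worsening AEs are fewer on it. Cancellation is only a possibility, and the rest of the safety evaluation is not undermined. This is a cheap improvement to the safety tables.

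**What to change.** In Protocol 12.3.7.1 and SAP 6.7.1:

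- Keep the all-AE comparison and state whether the test is on the pooled percentage or on each type of AE.
- Beside it, add the same any-AE and related-AE comparisons, and the severe-AE summary, excluding AD-worsening events.
- Define those events by a list of MedDRA preferred terms fixed before unblinding. SAP 6.3 already uses coded AD indications to identify rescue medication, so building such a list is routine.
- Show the number of subjects with AD-worsening AEs as a separate summary row, so that any drug-induced worsening stays visible.

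AE collection does not change. The cost is one term list agreed under blind, one extra set of table rows, and two sets of percentages to report and explain.
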